9.3.3. Key Secondary Endpoints

The key secondary analyses are:

- The proportion of participants who achieve an IGA score of cleared (0) at Week 16 will be compared between the JNJ-77242113 group and the placebo group.
- The proportion of participants who achieve a PASI 75 response at Week 4 will be compared between the JNJ-77242113 group and the placebo group.
- The proportion of participants who achieve a PASI 90 response at Week 8 will be compared between the JNJ-77242113 group and the placebo group.
- The proportion of participants who achieve a PASI 75 response at Week 16 will be compared between the JNJ-77242113 group and the placebo group.
- The proportion of participants who achieve a PASI 100 response at Week 16 will be compared between the JNJ-77242113 group and the placebo group.
- The proportion of participants who achieve an ss-IGA score of absence of disease (0) or very mild disease (1) and at least a 2-grade improvement from baseline at Week 16 will be compared between the JNJ-77242113 group and the placebo group among participants with a baseline ss-IGA score ≥ 2 .
- The proportion of participants who achieve PSSD symptom score of 0 at Week 8 will be compared between the JNJ-77242113 group and the placebo group among participants with a baseline PSSD symptom score > 0 .
- The proportion of participants who achieve at least a 4-point improvement from baseline in PSSD Itch score at Week 4 will be compared between JNJ-77242113 group and the placebo group among participants with baseline PSSD Itch score of ≥ 4 -points.
- The proportion of participants who achieve at least a 4-point improvement from baseline in PSSD Itch score at Week 16 will be compared between the JNJ-77242113 group and the placebo group among participants with a baseline PSSD Itch score ≥ 4 -points.
- The proportion of participants who achieve PSSD symptom score of 0 at Week 16 will be compared between the JNJ-77242113 group and the placebo group among participants with a baseline PSSD symptom score > 0 .
- The proportion of participants who achieve a PASI 75 response at Week 52 will be compared between the JNJ-77242113 group and the withdrawal group among PASI 75 responders randomized at Week 24.
- The proportion of participants who achieve a PASI 90 response at Week 52 will be compared between the JNJ-77242113 group and the withdrawal group among PASI 90 responders randomized at Week 24.
- The time to loss of PASI 75 response through Week 52 will be compared between the JNJ-77242113 group and the withdrawal group among PASI 75 responders randomized at Week 24.

- The time to loss of PASI 90 response through Week 52 will be compared between the JNJ-77242113 group and the withdrawal group among PASI 90 responders randomized at Week 24.

To evaluate the consistency of the efficacy, subgroup analyses of select key secondary endpoints based on demographics (eg, adolescents versus adults), baseline disease characteristics and previous psoriasis medications and therapies will be performed.

In order to control the overall Type I error rate ($\alpha=0.05$), multiplicity adjustment will be applied to the analyses of the co-primary endpoints and key secondary endpoints listed above. The multiplicity testing strategy will be devised based on the expected power and relative importance of the endpoints and will be performed via a graphical approach. A single SAP with a unified approach is targeted for this study. However, different regulatory authorities may require prioritization of different endpoints; detailed multiplicity-control procedures will only be defined in the SAP and not in the protocol.

The proportions of participants achieving a key secondary efficacy response will be summarized and compared between treatment groups in the same manner as the co-primary endpoints using the appropriate stratification factors. Similar data handling rules as the primary endpoints will be used for the key secondary binary endpoints. Specifically, composite strategy will be used for ICE 1-2 (as defined in Section 9.3.2) and/or ICE 4 (meeting retreatment criterion during the randomized withdrawal period; only applicable to Week 52 endpoints) where participants with those ICEs are considered as non-responders; treatment policy strategy will be used for ICE 3 (Section 9.3.2) where observed data will be used. After application of ICEs, participants with missing data will be imputed as non-responders. The same statistical method as that for the co-primary endpoints using the appropriate stratification factors will be used for analyzing the binary endpoints using the appropriate stratification factors (ie, age group, baseline weight category for adults, and geographic region for endpoints during the placebo-controlled period and geographic regions and PASI 90 response status at Week 24 for Week 52 endpoints) (Section 9.3.2). The analyses related to the time to event endpoints during the randomized withdrawal period will be performed using log-rank test stratified by geographic region and PASI 90 response status at Week 24.

9.3.4. Other Secondary Endpoints and Exploratory Endpoints

Other secondary and exploratory endpoints are listed in Section 3. The analyses for other secondary and exploratory efficacy endpoints at Week 16 (comparisons between JNJ-77242113 and placebo) and at Week 52 (comparisons between the JNJ-77242113 group and the withdrawal group among participants randomized at Week 24) will be performed. No adjustments for multiple comparisons will be made and nominal p-values will be provided. Selected efficacy endpoints will also be summarized over time. A complete list of the planned analyses of other secondary and exploratory endpoints will be described in the SAP.

9.3.5. Safety Analyses

Safety data, including but not limited to, AEs, SAEs, AESIs (active TB, malignancy, possible Hy's Law cases), discontinuation of study intervention due to AEs, changes in laboratory assessments, changes in vital signs, and changes in weight, changes in PHQ-9 scores, and changes in C-SSRS

will be summarized. Treatment-emergent AEs will be summarized by treatment group and MedDRA system organ class and preferred terms. Details will be specified in the SAP.

All safety analyses will be performed using the Safety Analysis Set; participants will be summarized by the intervention they received.

Adverse Events

The verbatim terms used in the CRF by investigators to identify AEs will be coded using the MedDRA. Any AE occurring at or after the initial administration of study intervention or that is a consequence of a pre-existing condition that has worsened since baseline is considered to be treatment emergent. All reported treatment-emergent AEs will be included in the analysis. For each AE, the percentage of participants who experience at least 1 occurrence of the given event will be summarized by intervention group.

The following analyses will also be used to assess the safety of participants in the study:

- The incidence and type of AEs.
- The incidence and type of SAEs.
- The incidence and type of AESIs.
- The incidence and type of severe AEs.
- The incidence and type of treatment-related AEs and SAEs as assessed by the investigator.
- The incidence and type of AEs leading to discontinuation of study intervention.

Listings of participants with SAEs, severe AEs, AEs of psoriasis, AESIs and AEs leading to discontinuation of study intervention will also be provided. Summaries, listings, datasets, or participant narratives may be provided, as appropriate, for those participants who die, who discontinue intervention due to an AE, or who experience a severe or a SAE.

Clinical Laboratory Tests

Laboratory data will be summarized by type of laboratory tests. Selected laboratory parameters will be summarized by treatment group. Common Terminology Criteria for Adverse Events (CTCAE) and ULN will be used to identify abnormal laboratory test results, and the incidence and severity of abnormal laboratory parameters (hematology and chemistry) will be summarized by treatment group.

In addition, a listing of participants with Grade 2 or higher laboratory test results (based on the CTCAE criteria) will also be provided.

Reference ranges and markedly abnormal results (specified in the SAP) will be used in the summary of laboratory data. Descriptive statistics will be calculated for all selected laboratory analyte at baseline and for observed values and changes from baseline at each scheduled time point.

Vital Signs

Vital signs including temperature, pulse/heart rate, and blood pressure (systolic and diastolic) will be summarized at selected scheduled timepoints using descriptive statics.

Weight

Weight and height will be summarized over time using descriptive statistics for adolescent participants. Weight will be summarized over time using descriptive statistics for adult participants.

Tanner Staging

Count and percentage of Tanner scale (range from Stage 1 to Stage 5) will be summarized by gender and age group for adolescent participants.

PHQ-9

Depression severity based on the PHQ-9 will be summarized descriptively by treatment group.

C-SSRS

Suicide-related thoughts and behaviors based on the C-SSRS will be summarized descriptively by treatment group.

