Study Procedure																
ss-IGA		X			X		X		X			X		X		W8-W52: collect only for participants with active scalp psoriasis at W0.
sPGA-G		X			X		X		X			X		X		W8-W52: collect only for participants with active genital psoriasis at W0.
hf-PGA		X			X		X		X			X		X		W8-W52: collect only for participants with active palmoplantar psoriasis at W0.
f-PGA		X			X		X		X			X		X		W8-W52: collect only for participants with active nail psoriasis at W0.
mNAPSI		X			X		X		X			X		X		
PGA of Disease Activity		X			X		X							X		Only for participants <18 years of age with a previous diagnosis of PsA at or before screening.
Photography (optional substudy)		X		X			X									
Safety Assessments																
Full physical examination	X	X												X		
Targeted physical examination			X	X	X	X	X	X	X	X	X	X	X			Recommended to include skin and general exam with additional organ systems based on investigator's judgement.
Tanner Staging		X												X		W52: Only for participants <18 years old at screening with previous Tanner stage <5.
Height	X	X					X							X		At screening, W16 and W52: Only for participants <18 years at Screening.
Weight	X	X					X							X		At screening: Only for participants <18 years of age.

Period	Screen-ing	Placebo-controlled					JNJ-77242113 Treatment		Randomized withdrawal and retreatment						Unsch-eduled ^{a,b}	Notes: See Section 1.3.2 for Early Termination Visit procedures.
Week (W)	-5-0	0	2	4	8	12	16	20	24	28	32	36	44	52		
Visit Window (days)			±2	±2	±4	±4	±4	±4	±4	±4	±4	±4	±4	±4		
Study Procedure																
Vital signs	X	X	X	X	X	X	X	X	X	X	X	X	X	X	X	Including temperature, heart rate, respiratory rate, and blood pressure.
12-lead triplicate ECG	X						X							X		
PHQ-9	X	X	X	X	X	X	X	X	X	X	X	X	X	X		
C-SSRS	X	X	X	X	X	X	X	X	X	X	X	X	X	X		
TB evaluation	X	X	X	X	X	X	X	X	X	X	X	X	X	X	X	
Pregnancy test for female participants of childbearing potential	X (serum)	X	X	X	X	X	X	X	X	X	X	X	X	X		A negative urine test result is required at each visit prior to dispensing study intervention. A urine pregnancy test may be performed at any time during the visit including before PROs.
Clinical Laboratory Tests																
Hematology	X	X		X	X	X	X	X	X	X	X	X	X	X		
Chemistry	X	X		X	X	X	X	X	X	X	X	X	X	X		
Lipid panel		X					X							X		Fasting requirement: ≥6 h unless medically contraindicated.
hs-CRP		X					X							X		
Urinalysis		X		X	X	X	X	X	X	X	X	X	X	X		May be performed any time during the study visit including before PRO collection.

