1.3.2. Schedule of Activities – Open Label Treatment

Period	Open-label Treatment									Safety Follow-up	Early Termination ^a	Notes:
Week (W)	64	76	88	100	112	124	136	148	156	160		
Visit Window (days)	±6	±6	±6	±6	±6	±6	±6	±6	±6	±6		
Study Procedure												
Study Intervention Administration												
Dispense study intervention	X	X	X	X	X	X	X	X				
Administer study intervention	Oral study intervention will be self-administered daily (Section 6.1).											
Study intervention accountability	X	X	X	X	X	X	X	X	X		X	
Efficacy Assessments												
PROs: Complete in the order shown before any tests, procedures, or consultations for all visits unless otherwise noted.												
PSSD (7-day recall)	X	X	X	X	X	X	X	X	X		X	
DLQI or CDLQI	X	X	X	X	X	X	X	X	X		X	
GenPs-SFQ	X		X		X		X		X		X	Collect only for participants with active genital psoriasis at W0. Only for participants ≥18 years of age.
PROMIS-29 or PROMIS-25	X		X		X		X		X		X	PROMIS-25 is only for participants <18 years of age.
PsA Pain Assessment	X		X		X		X		X		X	Collect only for participants with a diagnosis of PsA at or before screening.
PsA Disease Activity Assessment	X		X		X		X		X		X	
ClinROs												
IGA	X	X	X	X	X	X	X	X	X		X	
PASI	X	X	X	X	X	X	X	X	X		X	
BSA	X	X	X	X	X	X	X	X	X		X	
ss-IGA	X		X		X		X		X		X	Collect only for participants with active scalp psoriasis at W0.
sPGA-G	X		X		X		X		X		X	Collect only for participants with active genital psoriasis at W0.

Period	Open-label Treatment									Safety Follow-up	Early Termination ^a	
	Week (W)	64	76	88	100	112	124	136	148	156	160	
Visit Window (days)	±6	±6	±6	±6	±6	±6	±6	±6	±6	±6	±6	
Study Procedure												Notes:
hf-PGA	X		X		X		X		X		X	Collect only for participants with active palmoplantar psoriasis at W0.
f-PGA	X		X		X		X		X		X	Collect only for participants with active nail psoriasis at W0.
mNAPSI	X		X		X		X		X		X	
Safety Assessments												
Full physical examination					X					X	X	
Targeted physical examination	X	X	X	X			X	X	X		X	Recommended to include skin and general exam with additional organ systems based on investigator's judgement.
Tanner Staging					X					X		Only for participants <18 years old at Screening with previous Tanner stage <5.
Height					X					X		Only for participants <18 years old at screening.
Weight					X					X	X	
Vital signs	X	X	X	X	X	X	X	X	X	X	X	Including temperature, heart rate, respiratory rate, and blood pressure.
12-lead triplicate ECG					X					X	X	
PHQ-9	X	X	X	X	X	X	X	X	X	X	X	
C-SSRS	X	X	X	X	X	X	X	X	X	X	X	

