2.3.3. Benefit-risk Assessment for Study Participation

The measures taken to minimize risk to participants of this study, the potential risks identified in association with JNJ-77242113 are justified by the anticipated benefits that may be afforded to participants with moderate to severe plaque psoriasis.

Direct benefits and risks for adolescent participants have not been established in previous clinical trials of JNJ-77242113, but because adult and adolescent moderate to severe plaque psoriasis patients share similar clinical manifestations, histological features, and anticipated response to JNJ-77242113 the benefit and risks to study participation for adults and adolescents are anticipated to be the same (Section 2.1 Study Rationale).

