4. STUDY DESIGN

4.1. Overall Design

This is a Phase 3 randomized, double-blind, placebo-controlled, parallel-group, multicenter interventional study with randomized withdrawal and retreatment in participants with moderate to severe plaque psoriasis.

A target of 600 participants will be enrolled in this study. Approximately 540 adults and 60 adolescent participants will be randomized with a 2:1 randomization ratio to JNJ-77242113 200 mg or placebo. Randomization will be separately performed for adult and adolescent groups. Within the adult group, randomization will be further stratified by baseline weight category (≤ 90 kg, >90 kg) and geographic region. Within the adolescent group, randomization will be further stratified by geographic region.

- Adult participants
 - JNJ-77242113 200 mg once daily
 - Week 0 to Week 24: Participants will be treated with JNJ-77242113 200 mg once daily
 - Week 24 to Week 52:
 - Participants who are PASI 75 responders or IGA 0 or 1 responders (ie, those who achieve an IGA score of 0 or 1 and have ≥ 2 -grade improvement from baseline) at Week 24 will be re-randomized 1:1 to either continue JNJ-77242113 or to be transitioned to placebo. Participants transitioned to placebo will be retreated with JNJ-77242113 200 mg once daily upon loss of $\geq 50\%$ of Week 24 PASI improvement or starting at Week 52 if loss of response is not observed. All participants will be treated with JNJ-77242113 at Week 52.
 - Participants who are both PASI 75 non-responders and IGA 0 or 1 non-responders at Week 24 will continue to receive JNJ-77242113 200 mg once daily through Week 52.

- Week 52 to Week 156: Participants will receive JNJ-77242113 200 mg once daily through Week 156.
- Placebo to JNJ-77242113 200 mg once daily
 - Week 0 to Week 16: Participants will receive placebo once daily through Week 16.
 - Week 16 to Week 156: Participants will cross-over to receive JNJ-77242113 200 mg once daily through Week 156.
- Adolescent participants
 - JNJ-77242113 200 mg once daily
 - Week 0 to Week 156: Participants will be treated with JNJ-77242113 200 mg once daily
 - Adolescents will not participate in re-randomization regardless of their PASI score or IGA score at Week 24.
 - Placebo to JNJ-77242113 200 mg once daily
 - Week 0 to Week 16: Participants will receive placebo once daily through Week 16.
 - Week 16 to Week 156: Participants will cross-over to receive JNJ-77242113 200 mg once daily through Week 156.

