8.3.1. Vital Signs

Temperature, pulse/heart rate, respiratory rate, blood pressure will be assessed.

Blood pressure and pulse/heart rate measurements will be assessed in a seated position preceded by at least 5 minutes of rest in a quiet setting without distractions (eg, television, cell phones) with a completely automated upper arm cuff device. Manual techniques will be used only if an automated device is not available.

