#### **4.5. Safety Analyses**

All safety analyses will be performed using safety analysis set based on actual intervention received. No formal statistical comparison is planned.

For all continuous safety variables, descriptive statistics by intervention group will include the N, mean, standard deviation, median, minimum, and maximum. Categorical variables will be summarized by intervention group using frequency counts and percentages.

The cumulative safety data will be analyzed through different study periods as shown below. Unless otherwise specified, tabular summaries of safety events are also presented as following:

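### Minor: adolescent height and weight are summarised without reference to age and sex, although adolescents have no concurrent control after Week 16; a height z-score would be easier to read

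*Protocol*

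**What the plan says.** Protocol 9.3.5 (Weight) gives the growth analysis in one sentence: "Weight and height will be summarized over time using descriptive statistics for adolescent participants". The opening of the same section includes changes in weight among the safety data and defers the rest: "Details will be specified in the SAP". A separate paragraph tabulates Tanner stage by gender and age group.

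SAP 4.5.3 covers laboratory tests, vital signs, C-SSRS, Tanner staging, PHQ-9 and ECG. It has no post-baseline height or weight summary. Its Tanner table is by gender, for adolescents whose previous stage was below 5. Height and weight do not enter through vital signs, which Protocol 8.3.1 defines thus: "Temperature, pulse/heart rate, respiratory rate, blood pressure will be assessed"; SAP Table 8 lists neither. What remains is the general rule in SAP 4.5: "For all continuous safety variables, descriptive statistics by intervention group will include the N, mean, standard deviation, median, minimum, and maximum".

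Height is measured at Week 0 in everyone. For the other visits up to Week 52 the schedule in Protocol 1.3.1 says: "At screening, W16 and W52: Only for participants <18 years at Screening". The open-label schedule (1.3.2) has two further height measurements, also limited to participants under 18 at screening. The extracted table does not show reliably which weeks these are.

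For adolescents randomised to placebo, Protocol 4.1 says: "Week 16 to Week 156: Participants will cross-over to receive JNJ-77242113 200 mg once daily through Week 156". The same section excludes all adolescents from the Week 24 re-randomisation.

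**The concern.** Adolescents grow during a three-year study whether or not they take the drug. While a placebo group runs alongside, expected growth cancels in the comparison. After Week 16 it does not. A mean gain in centimetres or kilograms then depends on which ages and sexes were enrolled, and a reader cannot tell from it whether growth was normal, slowed or accelerated. Relating each value to what is expected for age and sex would supply the missing yardstick.

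At stake is how well one descriptive safety table for a small subgroup can be read. The protocol gives a reason to want it readable: "Direct benefits and risks for adolescent participants have not been established in previous clinical trials of JNJ-77242113". No efficacy conclusion depends on it.

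**Working it through.** The documents state no figure for adolescent growth, so there is none to reproduce.

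**Inputs.** About 60 adolescents, randomised 2:1 (Protocol 4.1): 60 × 2/3 = 40 active and 60 × 1/3 = 20 placebo. Crossover is at Week 16, treatment ends at Week 156, and there is no adolescent re-randomisation (Protocol 4.1). Post-baseline heights are at Week 16, Week 52 and two later open-label visits (Protocol 1.3.1 and 1.3.2).

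**1. How much of the follow-up lacks a control.** (156 − 16)/156 = 140/156 = 90% of the treatment weeks. Of four post-baseline height visits, only Week 16 is controlled, so three of four are not.

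**2. Whether the original arms can stand in as a comparison later.** If dosing continues, exposure at week w is w weeks in the active arm and w − 16 in the crossover arm.

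| Time | Active from Week 0 | Crossover at Week 16 | 16 weeks as share of the longer exposure |
|---|---|---|---|
| Week 52 | 52 weeks | 36 weeks | 16/52 = 31% |
| Week 156 | 156 weeks | 140 weeks | 16/156 = 10% |

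Both arms take the drug and their exposures converge in relative terms, so this contrast says little about a sustained effect. SAP 4.5 also pools them: the safety summary through Week 52 adds a combined JNJ-77242113 group, in which crossover participants contribute data from Week 16 onward, and the summary through Week 160 is for exposure to the drug.

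**3. Sampling error, in SDs of the change.** These are 95% half-widths with no dropout assumed.

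- Week 16 contrast: 1.96 × √(1/40 + 1/20) = 0.54 SD.
- Later single-group mean: 1.96/√40 = 0.31 SD for n = 40, or 1.96/√60 = 0.25 SD for n = 60. The n = 60 figure pools arms with unequal exposure.

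Using t quantiles gives 0.55, 0.32 and 0.26. The later mean can be estimated, but the plan gives nothing to hold it against.

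**4. What standardising might gain in precision (assumptions only).** The documents give no SD for growth. Suppose age and sex explain a share R² of the variance in 52-week height change. The half-width then shrinks by √(1 − R²): to 84%, 71% or 55% of the raw one for R² = 30%, 50% or 70%. With an assumed SD of 3 cm and n = 40, the raw half-width is 1.96 × 3/√40 = 0.93 cm, falling to 0.78, 0.66 or 0.51 cm. Over SDs of 2 to 4 cm, the raw half-width is 0.62 to 1.24 cm and the standardised one 0.34 to 1.04 cm.

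Steps 1 to 3 describe the design. They do not measure the benefit of the fix. Step 4 does so only under assumed inputs, and the main benefit, having a yardstick at all, is not a matter of precision.

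**The case against.** The strongest reply is that this is one more descriptive table. No formal safety comparison is planned, so prespecification guards against little, and z-scores could be derived later from the same data. Growth is not ignored either: Tanner staging is planned, changes in weight are listed, and physical examinations recur, with new clinically significant findings recorded as adverse events (Protocol 8.1.1). Most of this stands, and it is why the point is minor. It does not remove the point. The Tanner table is separate from height, neither it nor weight change is standardised growth, and naming the reference in advance avoids choosing one after seeing the data.

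Three stronger readings are tempting and unsupported.

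- A reader might infer that the SAP drops adolescent growth altogether. The general rule in SAP 4.5 would still produce raw tables, so the weakness is the choice of measure.
- A reader might infer a suspected growth risk. The documents name none: the drug risks in Protocol 2.3.1 are hypersensitivity, anti-drug antibodies and infection, and the events of special interest are active tuberculosis, malignancy and possible Hy's Law cases. The sentence quoted from 2.3.3 goes on to expect the same benefits and risks in adolescents as in adults.
- A reader might infer that z-scores would isolate a drug effect. They remove average growth for age and sex but do not adjust for pubertal timing, and an external reference is not a randomised control.

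**Conclusion.** The concern holds as a minor improvement to a descriptive safety readout. The plan gives unstandardised height and weight summaries, and for 90% of the treatment weeks and three of the four post-baseline height visits adolescents have no concurrent control against which to read them. A standardised height change is a better measure for that period and uses measurements already scheduled. Sample size, alpha, power and every endpoint are unaffected.

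The conclusion rests on about 60 adolescents enrolling at 2:1 and on the visit count in the schedules. It does not depend on the exact weeks of the two open-label heights. Any numerical gain in precision depends on an assumed SD and an assumed share of variance explained by age and sex, neither of which the documents provide.

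**What to change.** In SAP 4.5.3, for participants under 18 at screening, add change from baseline in age- and sex-standardised height z-score as the main growth readout, with weight and BMI z-scores as support. Name one growth reference before the Week 24 database lock. Show the results by arm at Week 16 and then at each scheduled height and weight visit, alongside the raw values, and read them with Tanner stage.

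The cost is one SAP paragraph and one table, with no new visit or measurement. Age at each measurement is needed more finely than whole years. The documents show demographics at screening and age in years, so the sponsor should confirm that this can be derived.

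The downsides are modest:

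- One external reference has to serve three regions and participants who pass 18 during the study (at most about 18 + 165/52 = 21 years).
- Z-scores do not adjust for pubertal timing, which is why Tanner stage should sit beside them, and they do not replace a control arm.
- The 40 kg entry minimum for adolescents (Protocol 5.1, criterion 7) may cause some regression to the mean in weight and BMI z-scores, so height should lead.
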